9.3 Adverse Events of Special Interest

The following adverse events of special interest must be reported to the Sponsor within 24 hours of the Investigator's awareness, even if not meeting the definition of a serious adverse event:

- Severe infusion-related reactions (see [Section 8.2](#)).
- Hypersensitivity reaction during the Study Drug infusion (see [Section 8.2](#)).
- Anaphylaxis (see [Section 8.2](#)) occurring at any time, even if considered unrelated to the Study Drug

A CRF for the collection of the details of such reactions will be available in the EDC.

Neutropenia, Grade 2 or higher [i.e., absolute neutrophil count < 1500/mm³ and decline by at least 25% from Baseline] are also events of interest and these will be separately summarized by treatment group and dose.

9.4 Assessment of Causal Relationship

The causal association of AEs to Study Drug administration should be determined as follows:

The following categories should be used in the causality assessment of suspected adverse reactions:

Probable

The AE:

- follows a reasonable temporal sequence from the time of Study Drug administration; and/or
- follows a known response pattern to the Study Drug; and
- was unlikely to have been produced by other factors such as the patient's clinical state, therapeutic intervention or concomitant therapy.

Possible

The AE:

- follows a reasonable temporal sequence from the time of Study Drug administration; and/or
- follows a known response pattern to the Study Drug; but
- could have been produced by other factors such as the patient's clinical state, therapeutic intervention or concomitant therapy.

Unlikely

The AE:

- does not follow a reasonable temporal sequence from the time of Study Drug administration; and
- was most likely produced by other factors such as the patient's clinical state, therapeutic intervention or concomitant therapy.

Unrelated

This category is applicable to those AEs that are judged to be clearly and incontrovertibly due only to extraneous causes (the patient's clinical state, therapeutic intervention or concomitant therapy) and do not meet the criteria for Study Drug relationship listed under Probable, Possible, or Unlikely.

An AE with causal relationship not initially determined will require follow-up to assign causality.

9.5 Assessment of Severity

The Investigator must determine the severity of the event according to CTCAE version 4.03. Severity describes the intensity of the adverse event.

For events not covered by the CTCAE, will be qualitatively described as below and mapped as Grade 1 through 5 as shown for analysis purposes.

Mild (Grade 1)	Awareness of sign or symptom, but easily tolerated
Moderate (Grade 2)	Discomfort enough to cause interference with normal daily activities
Severe (Grade 3)	Inability to perform normal daily activities
Life Threatening (Grade 4)	Immediate risk of death from the reaction as it occurred
Fatal (Grade 5)	Event resulted in death

9.6 Adverse Event Reporting

The AE reporting period starts with the signing of the Long ICF and continues through the Week 24 study visit, other than for AEs believed to be related to study procedures, which should be recorded starting with the signing of the Short ICF. Patients in this study who experience a drug-related AE or SAE will be followed until the AE or SAE is resolved or stabilizes per the Investigator's judgment, even if this occurs after the final study visit. All AEs spontaneously reported by the patient and/or in response to an open question from study personnel or revealed by observation, physical examination, or other diagnostic procedures will be recorded and reported on the appropriate CRF. When a unifying diagnosis has been made that accounts for several possible signs and/or symptoms, the unifying diagnosis should be selected as the AE term. For example, the combination of general malaise, mild fever, headache, and rhinitis should be described as "upper respiratory syndrome" if this diagnosis has been made, rather than reporting the individual symptoms as separate events.

If any laboratory test is newly abnormal during the course of the study, it will be followed at the discretion of the Investigator. Abnormalities of laboratory tests which are, in the opinion of the Investigator, clinically significantly worse compared to prior to the signing of the Long ICF, or for which a medical intervention is initiated, should be reported as AEs on the AE CRF.

9.7 Reporting of Serious Adverse Events and Adverse Events of Special Interest

The SAE reporting period is the same as the AE reporting period. All SAEs that occur during the reporting period and regardless of causality, must be reported by the Investigator to [REDACTED] by completing the SAE Form in the electronic data capture (EDC) system. Any pertinent source documents should also be submitted as soon as they are available. Do not withhold submission of an SAE even if complete information about the event is not available at the time of the initial report. Follow-up information on the SAE should be sent promptly by the Investigator when any additional relevant information about the event becomes known to the Investigator, or as requested by [REDACTED] or Corvidia Therapeutics.

SAE and Pregnancy Reporting Contact Information

Hypersensitivity reactions (see [Section 8.2](#)) occurring during the Study Drug infusion and anaphylaxis occurring anytime during Weeks 1 – 24 of the study should be reported as adverse or serious adverse events within the EDC AE and SAE CRFs within 24 hours of the site's awareness of the event. A supplemental CRF will also be completed for such events. Please submit as much information as is available with the initial report.

Corvidia Therapeutics will immediately notify the Investigator about important safety or toxicology information as it becomes available. It is the responsibility of the Investigator to promptly notify the IRB/ IEC about new and relevant safety information regarding the Study Drug, including serious adverse drug reactions involving risk to human subjects, in accordance with the applicable policies. An unexpected event is one that is not listed by nature or severity in the [Investigator's Brochure](#).

9.8 Pregnancy Reporting

If a woman who is a study patient becomes pregnant or a woman suspects she is pregnant from a male study patient, the Investigator should be informed immediately. The Sponsor must, in turn, also be notified by the Investigator immediately by completing a Pregnancy Form and faxing or emailing it to [REDACTED] (see [Section 9.7](#)). The pregnancy must be followed up through delivery or other fetal outcome. For any abnormal fetal outcome, including congenital anomaly or birth defect, spontaneous or therapeutic abortion, still birth, pre-mature birth, or other outcome other than live normal birth, the Investigator should promptly report to the Sponsor the abnormal fetal outcome on an SAE form.

10 STUDY ASSESSMENTS

10.1 Pharmacodynamic Assessments

10.1.1 Cardiac Magnetic Resonance Imaging for LV Mass Index

Magnetic resonance imaging will be used to characterize cardiac left ventricular mass index. Methodology for this assessment will be specified via a separate imaging protocol and MRI Technical Manual.

10.1.2 Handgrip Test

The handgrip test is a measure of strength. The methodology is described in the Study Reference Manual.

10.2 Safety Assessments (other than Adverse Events)

10.2.1 Vital Signs

Vital signs include temperature, respiratory rate, heart rate, and blood pressure. Whenever possible, vital signs will be obtained after at least 5 minutes in the sitting position or, when necessary, in a semi-recumbent position.

10.2.2 12-lead ECG

At specified time points, standard 12-lead ECG will be recorded in the supine position (or with the patient as flat as possible). The ECG will be locally read by the Investigator.

10.2.3 Physical Examination

Scheduled (limited) physical exams must include at a minimum an examination of the skin, oropharynx, lungs, heart, abdomen, extremities (including feet), and any areas suggested by symptoms, with particular attention to signs of infection.

10.2.4 Stool Occult Blood Testing

Stool fecal occult blood testing will be performed at Screening and analyzed by the central lab. If needed to meet Screening timelines, one or more stool tests may be performed locally.

10.2.5 Clinical Laboratory Testing

Details on the collection, processing, storage, and shipment of central lab samples are contained in the Laboratory Manual. The list of laboratory parameters can be found in [Appendix E](#), Local Laboratory assessments are described below.

The following tests will be performed at the Local Laboratory:

- Coagulation: INR (only for patients on warfarin)
- Stool occult blood (if needed)

11 STATISTICAL CONSIDERATIONS AND DATA ANALYSIS

The study design and objectives are described in [Sections 2.0](#) and [3.0](#), respectively.

11.1 Sample Size

The primary objective of this study is to determine the maximum tolerated dose. The MTD will be exceeded and stopping criteria for that dose will have been met if more than 2 of 8 COR-001-treated patients in a cohort experience a DLT ($\geq 25\%$). With 8 patients dosed in each cohort and at the expected DLT rate of 25%, the probability of observing 2 or more patients with DLT is greater than 63% and the probability of observing at least 1 patient with DLT is 90%.

Sample size calculations were performed for hsCRP, TSAT, and CHr based on the literature ([Coyne 2007](#) and [Sieper 2013](#)). For 80% power to observe an hsCRP difference from placebo of -10.6 mg/dL with a common standard deviation of 17.3 the sample size required is 43 patients in each group. With effect sizes ranging from 0.46 to 0.77, the sample size ranges from 76 to 28. patients. The sample size with 80% power required to observe a TSAT difference of 5.7 with a common standard deviation of 6.4 (effect size of 0.89) is 21 patients, with effect sizes ranging from 1.12 to 0.67 requiring 28 to 76 patients. The sample size with 80% power required to observe a CHr difference of 0.9 pg with a common standard deviation of 1.92 is 73, with effect sizes ranging from 0.59 to 0.35 requiring sample size from 47 to 128 patients. All sample size calculations were done with two sided t-tests and a significance level of $\alpha = 0.05$.

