3.2 Study Schematic

Figure 2 Dose Escalation Schematic

- ¹ If the MTD is not exceeded, dose escalation may continue.
- ² If the MTD is exceeded, a lower dose, including previously studied dose, may be selected.

The MTD assessment will be based on safety data from Weeks 1 to 3. If more than 2 of 8 active patients in a cohort experience a DLT, the MTD will be considered to have been exceeded.

The planned doses shown here may be adjusted based on accruing PK, PD, and safety data. The highest dose that will be studied is a cumulative dose of 360 mg. Expansion cohorts to further evaluate doses below the dose that exceeded the MTD may be initiated at any time.

The randomization ratio within each cohort will be 8:2 (COR-001 to placebo).

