4.4 Dose-Limiting Toxicities, Maximum Tolerated Dose, and Stopping Rules

Prior to dose escalation (i.e., higher total dose than studied in the preceding cohorts), there will be a formal safety review by the Safety Review Committee. The safety review required for dose escalation will include 21 days of treatment data from the preceding cohort(s).

Dose-Limiting Toxicities are defined as follows:

1. Confirmed Grade 3 neutropenia and representing a decline of > 25% from baseline
2. Serious adverse events of infection in the presence of confirmed Grade 2 or higher new onset lymphopenia or new onset neutropenia.
3. \geq Grade 3 ALT or AST
4. \geq Grade 4 hematologic toxicity
5. \geq Grade 3 non-hematologic toxicity

DLT will be defined as any toxicity the relationship of which to the investigational agent cannot be ruled out as follows:

- With the exception of Grade 3 non-hematologic events, Grade 3 (or higher) CTCAE toxicity of above events having an assessed relationship to the Study Drug of “definitely”, “probably”, “possibly”, or “unlikely” will be considered DLTs.

Note: “non-hematologic events” refer to DLT criteria 1, 2, 3, and 5 above.

- Grade 3 non-hematologic toxicities having an assessed relationship to the Study Drug of “definitely”, “probably” or “possibly” will be considered DLTs.

In addition, dose-escalation may be halted for any safety trend believed to be dose-related that would pose an unacceptable risk if dose were escalated.

If more than 2 of 8 COR-001-treated patients in a cohort experience a DLT, the MTD will be exceeded and stopping criteria for that dose will have been met.

In addition, if 1 of 8 COR-001-treated patients in a cohort experiences a Grade 4 or 5 DLT, the dose will not be escalated.

Stopping Rules for Individual Patients

Severe (i.e., \geq Grade 3): infusion-related reactions, cardiopulmonary infusion reactions, anaphylaxis, or hypersensitivity (see [Section 8.2](#))

Stopping Rules for the Entire Study

If ≥ 5 COR-001-treated patients develop anaphylaxis at any point during the entire study, enrollment and further dosing will be stopped.

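### The MTD rule needs 3 or more DLTs in 8 patients, but the plan's 25% label and 63% probability describe 2 or more; the written rule gives 32%

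*Protocol*

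**What the plan says.** Protocol section 11.1 (Sample Size) names determination of the MTD as the primary objective and then makes three statements.

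- **Rule.** The MTD is exceeded, and the dose stopped, if "more than 2 of 8 COR-001-treated patients in a cohort experience a DLT".
- **Label.** A parenthesis directly after the rule expresses it as 25% or more.
- **Justification.** "With 8 patients dosed in each cohort and at the expected DLT rate of 25" percent, "the probability of observing 2 or more patients with DLT is greater than 63" percent. The chance of at least one DLT is given as 90%.

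SAP section 1.3.2 has the same paragraph. The rule also stands, without the label or the probabilities, in Protocol section 4.4 ("If more than 2 of 8 COR-001-treated patients in a cohort experience a DLT, the MTD will be exceeded"), in Protocol section 3.2 ("If more than 2 of 8 active patients in a cohort experience a DLT, the MTD will be considered to have been exceeded") and under the dose-escalation schematic in SAP section 1.3.1.

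Protocol section 4.4 adds that a single Grade 4 or 5 DLT in a cohort bars further escalation, and that escalation may be halted for a worrying dose-related safety trend.

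**The concern.** The rule, its label and its probability sit together in one paragraph but do not describe the same event. The case where they conflict is a cohort with exactly 2 DLTs in 8: the rule says the MTD is not exceeded, while the label says the threshold has been met.

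Characterizing the MTD is the primary safety endpoint (Protocol 3.1.2, SAP 1.2.1). A reader of the sample-size section would conclude that a dose with a 25% DLT rate is declared above the MTD in nearly two cohorts out of three. Two probabilities are printed (2 or more, and at least 1), and neither is for the event that triggers the rule. The plan therefore gives no operating characteristic for its primary decision.

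The MTD decision also has later consequences. It determines which active cohorts are pooled for the pharmacodynamic analyses (Protocol 3.1.3 and 11.4.3, SAP 7), which doses may be expanded (Protocol 3.2), when all 10 patients may be randomized in parallel without sentinels (Protocol 3.3.1), and the earliest date of the interim analysis (Protocol 11.5).

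**Working it through.** **Inputs.** From Protocol 11.1: n = 8 actively treated patients per cohort and an assumed true DLT rate p = 0.25. From Protocol 4.4: the rule is more than 2 of 8, so X ≥ 3, where X is the number of patients with a DLT.

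**Model.** X ~ Binomial(8, p), with P(X = k) = C(8, k) p^k (1 − p)^(8 − k).

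**Terms at p = 0.25.**

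- P(X = 0) = 0.75^8 = 0.1001
- P(X = 1) = 8 × 0.25 × 0.75^7 = 0.2670
- P(X = 2) = 28 × 0.25² × 0.75^6 = 0.3115

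**The plan's own figures.**

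- P(X ≥ 1) = 1 − 0.1001 = 0.8999. The stated 90% reproduces.
- P(X ≥ 2) = 1 − 0.1001 − 0.2670 = 0.6329. The stated value of more than 63% reproduces, for 2 or more.

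**The rule as written.**

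- P(X ≥ 3) = 0.6329 − 0.3115 = 0.3215 (from unrounded terms).
- Probability that the MTD is not declared exceeded: 1 − 0.3215 = 0.6785.

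**The label.** 2/8 = 25% and 3/8 = 37.5%. The smallest observed rate that triggers the rule is 37.5%; a label of at least 25% fits a rule of 2 or more.

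**Other true rates.** Apart from 25%, the rates below are assumptions; the documents do not give them.

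| True DLT rate | P(3 or more), written rule | P(2 or more), event quoted |
|---|---|---|
| 10% | 0.038 | 0.187 |
| 20% | 0.203 | 0.497 |
| 25% | 0.321 | 0.633 |
| 30% | 0.448 | 0.745 |
| 40% | 0.685 | 0.894 |

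Solving P(X ≥ 3) = 0.633 gives p = 0.376. The written rule reaches the quoted 63% only when the true DLT rate is about 38%.

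**The case against.** The strongest reply is that nothing is miscalculated and the operative rule is clear. The 63% and the 90% are right for the events they name, the rule reads the same way everywhere, and 2 or more is never stated as a rule. The text does not say outright that 63% is the chance of declaring the MTD exceeded. All of this is true. But the 63% directly follows the rule and its 25% label, as the rationale for 8 patients, and that label is wrong for the rule on any reading.

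A second reply is that 25% is called the expected DLT rate, not a rate the rule must detect. Protocol 3.6 notes a high background of Grade 2 and 3 events in this population, so a 32% trigger rate may be acceptable. This stands as a limit on interpretation. The documents name no target toxicity rate, so 32% cannot be called a failure of the rule. It is still the figure a reader needs in order to judge the rule.

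A third reply is that other safeguards exist: the Grade 4/5 bar on escalation, the safety-trend halt, and unblinded review by the Safety Review Committee. They limit the risk to patients. None of them defines exceeding the MTD, none has a stated probability, and none explains the label or the 63%. Two Grade 3 DLTs in a cohort would not invoke the Grade 4/5 bar.

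**Conclusion.** The concern holds. For the rule as written, the percentage label should be at least 37.5% instead of at least 25%, and the probability of triggering it at a 25% DLT rate is 32% instead of 63%. The printed figure is about twice the correct one (0.6329 / 0.3215 = 1.97). At that rate, about 31% of cohorts would have exactly 2 DLTs, where rule and label disagree.

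These numbers assume 8 evaluable active patients per cohort, independent outcomes and a common DLT probability within the cohort. They cover only the MTD rule, not the separate bar on escalation. The finding is that the primary decision is misdescribed; it does not show that the rule itself is unsuitable.

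**What to change.** Keep the rule and correct the paragraph in Protocol 11.1 and SAP 1.3.2:

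- Relabel the threshold as 3 or more of 8, an observed rate of at least 37.5%.
- State that at a true DLT rate of 25% the probability of triggering the rule is 32%. The figures for 2 or more (63%) and at least 1 (90%) may stay if they are marked as descriptive and not as the rule.
- Preferably print the probability for the rule at true rates of 10%, 20%, 25%, 30% and 40% (0.04, 0.20, 0.32, 0.45, 0.68), so that readers can judge it without a single assumed rate.

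The cost is one paragraph in each document. The figure at 25% will be lower than the one now printed, and nothing else changes.

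If the sponsor did intend 2 or more of 8, that is a change to the stopping rule. It would have to be made in Protocol 3.2, 4.4 and 11.1 and in SAP 1.3.1 and 1.3.2, and its effect on cohorts already assessed would need to be addressed, since Amendment 3 reports actual doses for Cohorts 1 to 5. The correction above does not require it.

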
Sample Size
	
Approximately 60 (i.e., up to 6 cohorts, including expansion cohorts)

Study Centers	Approximately 15 study sites
Statistical Methods Analysis	
The following analysis Populations are defined for the different types of data analysis:
 
• Intent-to-treat (ITT) analysis population, the primary population for the disposition and baseline data summaries.• Pharmacodynamic analysis population, the population for the pharmacodynamic analyses.• Pharmacokinetics analysis population for PK analysis.• Per-protocol analysis population for pharmacodynamics analyses• Safety analysis population for the safety analyses. 
All study-collected data will be summarized by treatment group for the appropriate analysis population, using descriptive statistics. Descriptive statistics for continuous variables will include number of patients (n), mean, standard deviation (SD), median, quartiles (Q1 and Q3), minimum (min) and maximum (max) values. Analysis of categorical variables will include frequency and percentages.
 
Data from COR-001-treated patients from Cohorts not exceeding the MTD will be pooled and data from all placebo patients will be pooled for the pharmacodynamic endpoint analyses.
 
Descriptive analyses by dose in which all placebo patients are pooled will also be conducted.

LIST OF ABBREVIATIONS, DEFINITIONS, AND TERMS

Term	Definition
AE	Adverse event
ALT	Alanine aminotransferase
AST	Aspartate aminotransferase
AUC	Area under the curve
β-hCG	β -Human chorionic gonadotropin hormone
BMP	Bone morphogenic protein
BMPR	Bone morphogenic protein receptor
BP	Blood pressure
BUN	Blood urea nitrogen
CBC	Complete blood count
CHr	Reticulocyte hemoglobin concentration
CFR	Code of Federal Regulations
COR-001	Monoclonal antibody to IL-6
C _{max/min}	Maximum/minimum observed concentration
CRF	Case report forms
CRO	Contract research organization
DLT	Dose-Limiting Toxicity
Dialysis Start Time	The start time of dialysis is defined by the earliest time point recorded on the dialysis flow sheet (or equivalent) with a blood flow rate > 0
Dialysis End Time	Dialysis is considered completed when the dialysis machine shows 0 minutes remaining for the treatment. The end time of dialysis is defined by the latest time point recorded on the dialysis flow sheet (or equivalent) with a blood flow rate = 0 or last recorded blood flow rate, whichever is later.
ECG	Electrocardiogram

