3.5.4 Rationale for the Dose Regimens

The main goal of COR-001 dosing in the planned Phase 1/2 hemodialysis patient study is to attain and maintain serum COR-001 concentrations sufficient for $\geq 90\%$ IL-6 binding over the 3-month Treatment Period, with a secondary goal of reducing hsCRP to below 5 mg/L while keeping the highest planned dose more than 20-fold below the no adverse effect level (NOAEL) observed in primates.

Effects on IL-6 and hsCRP

Pharmacokinetic and PD models were created based on data from the Phase 1 trial in RA patients (Study D4430C00001) and used to simulate dosing regimens that achieve the above goals (Section 3.5.4). Based on these models, lower doses were needed to maintain serum COR-001 concentrations above the target value (i.e., that value required to achieve $> 90\%$ IL-6 binding) compared to those needed to normalize hsCRP (defined as $\text{hsCRP} < 5\text{mg/L}$) in a hypothetical hemodialysis population whose baseline hsCRP is at median and serum IL-6 level is above the median. hsCRP normalization in at least 1/3 patients is predicted for cumulative COR-001 dose of ≥ 12 mg, and is not predicted for all patients until cumulative doses of 60 mg or greater are achieved. The COR-001 dose regimens planned are itemized below. Lower doses (including previously studied doses) may be substituted for the planned doses in the table below based on accruing data. In addition, PK and PD results will be reviewed to assess the appropriateness of the next planned dose and to guide revision of the next dose to be evaluated, if necessary.

Dose Cohort	Dose Regimen	Number of Doses	Total Cumulative Dose
1	2 mg every 14 days	6	12 mg
2	6 mg every 14 days	6	36 mg
3	20 mg every 14 days	6	120 mg
4	60 mg every 14 days	6	360 mg

The planned doses all provide plasma IL-6 binding in excess of 90% for the duration of the study, while hsCRP normalization is expected to be attained in 1/3 of patients at the lowest dose, and in 3/3 patients at the highest dose. Full suppression of hsCRP is not believed to be required for beneficial effect on hematologic or iron parameters given the linear correlation between CRP and the degree of erythropoietic inefficiency (Bárány 1997).

As of Amendment 3, the actual doses (all given every 14 days) were 2 mg (Cohorts 1 and 4); 6 mg (Cohorts 2 and 3); 20 mg (Cohort 5).

Safety Margins

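### The 80%-power sizes in Protocol 11.1 and SAP 1.3.2 hold only for two equal groups; at the planned split of about 48 to 12, unadjusted power is about 46% for hsCRP and 30% for CHr, and neither document says so

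*Protocol*

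**What the plan says.** Protocol 11.1 opens with the MTD objective and the DLT probabilities for 8 treated patients per cohort. It then sizes three pharmacodynamic (PD) endpoints from published effects, and SAP 1.3.2 repeats the text:

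- hsCRP: "For 80% power to observe an hsCRP difference from placebo of -10.6 mg/dL", and "with a common standard deviation of 17.3 the sample size required is 43 patients in each group".
- TSAT: the size "required to observe a TSAT difference of 5.7 with a common standard deviation of 6.4 (effect size of 0.89) is 21 patients".
- CHr: a difference of 0.9 pg with SD 1.92 needs 73.

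"All sample size calculations were done with two sided t-tests", at the 5% level. The words that make the size per group appear only for hsCRP.

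The design is stated elsewhere. The Synopsis gives the sample size as "Approximately 60 (i.e., up to 6 cohorts, including expansion cohorts", and Protocol 3.2 says "The randomization ratio within each cohort will be 8:2 (COR-001 to placebo". Protocol 3.1.3 and SAP 7 pool the active patients from cohorts not above the MTD, and pool all placebo patients. SAP 7.1 and 7.2 fit an ANCOVA with dose as a factor and baseline as covariate, and report a difference from placebo, a 95% confidence interval and a p-value for each dose.

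On units, 11.1 gives the hsCRP difference in mg/dL, while Protocol 3.5.4 plans the doses "with a secondary goal of reducing hsCRP to below 5 mg/L".

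**The concern.** Protocol 3.5 sends the reader to 11.1 for the PD sample-size calculations, and 80% is the only PD power figure found there. It belongs to a layout with two equal groups, which this trial does not have. The placebo arm, about 12 patients, is smaller than all three stated sizes.

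What is at stake is how a null result is read. The change in hsCRP to Week 4 is a primary PD endpoint, and the PD data are meant to guide the future programme (Protocol 11.5, SAP 10.2). With power below one half, a true effect of the planned size on hsCRP or CHr would more often be missed than found at p < 0.05. Someone with only the 80% figure in mind could take a non-significant p-value as evidence of no effect.

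**Working it through.** **Inputs.** Differences, SDs, test and alpha come from Protocol 11.1. The split comes from the Synopsis and Protocol 3.2: six cohorts × 8 = 48 active, and six × 2 = 12 placebo. Cohorts per dose come from Protocol 3.5.4: 2 mg in Cohorts 1 and 4, 6 mg in Cohorts 2 and 3, 20 mg in Cohort 5. SAP 11 refers to a Cohort 6, but its dose is not stated.

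**Formula.** Let d = difference / SD, with n1 active and n0 placebo. The noncentrality is δ = d × √[n1·n0/(n1 + n0)] on n1 + n0 − 2 degrees of freedom. Power is the probability that a noncentral t exceeds the two-sided 5% critical value in absolute size.

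**Step 1: the plan's figures.** At 1:1 and 80% power:

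| Endpoint | d | n per group | Stated |
|---|---|---|---|
| hsCRP | 10.6/17.3 = 0.613 | 42.8 → 43 | 43 |
| TSAT | 5.7/6.4 = 0.891 | 20.8 → 21 | 21 |
| CHr | 0.9/1.92 = 0.469 | 72.4 → 73 | 73 |

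All three reproduce exactly, as per-group sizes for equal groups.

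**Step 2: the planned pooled split.** For 48 vs 12, n1·n0/(n1 + n0) = 576/60 = 9.6, which carries the information of 2 × 9.6 = 19.2 patients per group at 1:1. Set against 43, 21 and 73, this shows at once that TSAT nearly gets there and the other two do not. For hsCRP, δ = 0.613 × √9.6 = 1.90 against a critical value of 2.00, so power is 46%. TSAT gives 77% and CHr 30%.

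**Step 3: per-dose comparisons against 12 placebo.**

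| Active vs placebo | Equal-group equivalent | hsCRP | TSAT | CHr |
|---|---|---|---|---|
| 24 vs 12 | 16.0 | 39% | 69% | 25% |
| 16 vs 12 | 13.7 | 34% | 61% | 22% |
| 8 vs 12 | 9.6 | 25% | 46% | 16% |

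SAP 1.2.3 lists only 2, 6 and 20 mg. If Cohort 6 received one of these (an assumption), the active groups at 2/6/20 mg are 24/16/8, 16/24/8 or 16/16/16, before exclusions.

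**Step 4: differences detectable with 80% power at 48 vs 12.** Solving for d gives 0.92. Multiplied by each SD:

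- hsCRP: 0.9195 × 17.3 = 15.9, against 10.6 in the plan.
- TSAT: 0.9195 × 6.4 = 5.9, against 5.7.
- CHr: 0.9195 × 1.92 = 1.77 pg, against 0.9 pg.

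**Step 5: size for 80% power at 4:1.** This takes 27, 13 and 46 placebo patients, or totals of 135, 65 and 230 (five times each).

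**Unit.** Read literally, 10.6 mg/dL is 10.6 × 10 = 106 mg/L, while the target in 3.5.4 is below 5 mg/L. The power figures depend only on 10.6/17.3, so they do not change if difference and SD share a unit. Which label is right cannot be settled from the documents.

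**The case against.** **No 80% claim is made for this trial.** A reader might infer that the plan promises 80% power for its PD comparisons. The documents do not support that. N is built from cohorts, the primary objective is safety and the MTD, and 11.1 openly lists sizes that a 60-patient 8:2 study cannot reach. This stands: the fault is a missing link between the calculations and the design, not a false power claim.

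**Little turns on PD significance.** No success criterion is tied to p < 0.05, the interim analysis has no stopping rule, dose escalation does not depend on PD significance, the by-dose analyses are labelled descriptive and 95% confidence intervals are planned. This also stands and limits the severity. It does not remove the point, because SAP 7.1 and 7.2 still attach a p-value to each dose.

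**The SAP uses ANCOVA, not a t-test.** Correct. Pooling residual variance across doses adds little: 8 vs 12 rises from 25%/46%/16% to about 26%/48%/17%. Baseline adjustment could add more. Assuming that the stated SD is unadjusted and that baseline correlates with change at 0.3 to 0.6, power at 48 vs 12 is about 50–65% (hsCRP), 81–92% (TSAT) and 32–43% (CHr). Reaching 80% would need a correlation near √[1 − (0.613/0.92)²] = 0.75 for hsCRP and √[1 − (0.469/0.92)²] = 0.86 for CHr. No correlation is given, so the gain is unknown.

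**The 48 vs 12 split is approximate.** N is approximate and dropouts may be replaced, which could add a few patients. Excluding cohorts above the MTD, PD-population exclusions and unimputed missing values would take some away.

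**Conclusion.** The concern holds for hsCRP and CHr. The sizes in Protocol 11.1 and SAP 1.3.2 assume equal groups that the 8:2 design does not provide, and the power it does provide is stated nowhere. At about 48 vs 12, unadjusted t-test power for the plan's own effects is about 46% for hsCRP and 30% for CHr. The pooled TSAT shortfall, 77% against 80%, is immaterial, and a modest gain from covariate adjustment would remove it. Per-dose power is lower for all three endpoints.

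These figures rest on six full cohorts at 8:2, no exclusions or missing data, the effects and SDs of 11.1, and no baseline adjustment. The per-dose figures also depend on the unstated dose of Cohort 6.

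One might go further and conclude that the trial is too small or must be enlarged. The documents do not support that: PD is secondary to safety, and by Amendment 3 Cohorts 1 to 5 were already completed or under way. This is a should-fix matter of stating the design's properties correctly. The hsCRP unit mismatch is a label to reconcile and alters no power figure.

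**What to change.** In Protocol 11.1 and SAP 1.3.2:

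1. Replace the equal-group sizes with the power, or the 80%-detectable difference, at the planned pooled allocation. At 48 vs 12 the detectable differences are about 15.9 for hsCRP, 5.9 for TSAT and 1.77 pg for CHr.
2. Give the same for the per-dose comparisons, using the group sizes that follow from the dose given to Cohort 6.
3. Label all these as unadjusted t-test figures. If the sponsor has a baseline correlation, state it and add the ANCOVA figures.
4. State that non-significant PD p-values are to be read with their confidence intervals and not as evidence of no effect.
5. Reconcile the hsCRP unit between 11.1 (mg/dL) and 3.5.4 (mg/L), and write the unit beside the SD as well.

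The cost is one paragraph in each document. No patients, visits or analyses are added. The stated figures become less favourable.
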